1.2 BACKGROUND ON MSTT1041A

MSTT1041A is a first-in-class, fully human, IgG2 monoclonal antibody that binds to ST2, the receptor for IL-33, and inhibits human IL-33. Nonclinical testing confirms that the molecule has high receptor affinity and is non-activating.

Refer to the MSTT1041A Investigator's Brochure for details on nonclinical and clinical studies.

1.3 STUDY RATIONALE AND BENEFIT-RISK ASSESSMENT

MSTT1041A prevents the IL-33-induced signaling that galvanizes immune cells in inflammation. IL-33 is a member of the IL-1 family of cytokines. It is considered an "alarmin" or a damage-associated molecular pattern molecule, that is constitutively expressed on epithelial cells and released upon cell injury or stress from exposure to such exogenous stimuli as allergens, toxins, or infections. IL-33 activates various immune cells through its receptor ST2, also known as IL-1RL1 (Nabe 2014). Recently, the IL-33/ST2 pathway has been found to play an important role in allergic diseases such as AD, asthma, and allergic rhinitis (Ding et al. 2018). Once released from these cells, typically in response to stress or damage, IL-33 signals through a receptor complex containing the primary binding receptor ST2 and the co-receptor IL-1RAcP. Intracellular signaling induced by this complex promotes the inflammatory actions of ST2-expressing cells. A secreted soluble form of ST2 (sST2) arises from alternative splicing, is elevated in settings of inflammation, and acts as a decoy to bind and inhibit released IL-33 (Hayakawa et al. 2007). Mice genetically deficient in ST2 (ST2^{-/-}) are phenotypically normal and have been used as controls for mechanistic studies to demonstrate that IL-33-elicited responses *in vivo* are entirely dependent on ST2 (Kondo et al. 2008). ST2 is expressed on keratinocytes, endothelial cells, fibroblasts, and inflammatory cells (including Type 2 innate lymphoid cells, monocytes, natural killer cells, T lymphocytes, mast cells, basophils, and eosinophils) (Cevikbas and Steinhof 2012; Liew et al. 2016). Binding of IL-33 to ST2 can activate both Th1 and Th2 T-cell inflammation depending on the underlying milieu. Signaling via ST2 leads to release of multiple mediators including tumor necrosis factor (TNF)- α , interferon (IFN)- γ , IL-5, IL-6, IL-9, amphiregulin, and IL-13 (Martin and Martin 2016; Griesenauer and Paczesny 2017).

Du et al. (2016) showed that IL-33 is expressed in keratinocytes, endothelial cells, and infiltrating mononuclear cells of AD skin lesions. ST2 is expressed in the stratum spinosum and was localized to the cytoplasm, cellular membrane, and intercellular space. ST2 is further expressed on dermal infiltrating cells, endothelial cells, and

neutrophils that infiltrated the epidermis (Du et al. 2016). Triggers such as allergens, irritants, and staphylococcal enterotoxin B increase expression of IL-33 and ST2 (Savinko et al. 2012). Furthermore, IL-33 has been shown to play a crucial role in activating Type 2 innate lymphoid cells and by this, contributing to development of allergic skin inflammation (Salimi et al. 2013). Moreover, IL-33 downregulates the expression of the skin barrier molecule filaggrin (Seltmann et al. 2015; Ryu et al. 2016; Nygaard et al. 2017) and the β -defensin 2 expression in human primary keratinocytes (Alase et al. 2012), thereby, exacerbating the defect in the barrier against allergen penetration and the susceptibility to bacterial superinfection in acute AD.

The inflammatory pathways in chronic AD are complex and involve both Th1 and Th2 immune responses. *In vitro*, IL-33 has been shown to influence both the Th1 and Th2 pathway. IL-33 expression is induced by TNF- α and IFN- γ in human dermal fibroblasts, HaCaT keratinocytes, macrophages, and human umbilical vein endothelial cells. IL-33-induced dendritic cells promote the differentiation from naive Th cells into Th2 cells and maintain memory Th2 cells, leading to the increased production of IL-5, IL-9, and IL-13. Meanwhile, Th1 cells respond to IL-33 and induce the release of IFN- γ , therefore driving skin inflammation towards chronic responses (Ding et al. 2018).

By targeting ST2, MSTT1041A has the capacity to block inflammation downstream of IL-33 activation. This is expected to translate into benefit in patients with AD. The ability to blunt inflammation across the broad population represents a significant therapeutic advance and addresses an important unmet medical need.

MSTT1041A was not associated with toxicity at doses of up to 300 mg/kg SC or IV (highest dose evaluated) in 28-day and 6-month cynomolgus monkey toxicology studies. In addition, there were no MSTT1041A-related cardiovascular findings in a single-dose safety pharmacology study or in repeat-dose toxicity studies. In an *ex vivo* human tissue cross-reactivity immunohistochemistry study, no specific staining in any human tissues was observed. At the no-observed-adverse-effect level (300 mg/kg SC or IV), there are significant exposure margins over human exposures.

As reported in the MSTT1041A Investigator's Brochure, there are no identified risks associated with MSTT1041A. In three completed Phase 1 studies, there were no serious adverse events or adverse events that led to treatment discontinuation in healthy subjects who received single (n=70, Study 20110235; n=41, Study 20130177) or multiple (n=41, Study 20110236) doses of MSTT1041A at SC doses ranging from 2.1 to 560 mg and IV doses ranging from 210 to 700 mg.

A Phase IIb study with MSTT1041A in patients with severe asthma is currently ongoing (502 patients were randomized into a 52-week double-blind treatment period and received blinded study treatment [70 mg, 210 mg, or 490 mg of MSTT1041A, or placebo]). Refer to the MSTT1041A Investigator's Brochure for a complete summary of safety information.

Thus, the favorable safety profile to date supports further development of MSTT1041A in patients with AD.

2. OBJECTIVES AND ENDPOINTS

This study will evaluate the efficacy, safety, and pharmacokinetics of MSTT1041A compared with placebo in patients with moderate to severe AD. Specific objectives and corresponding endpoints for the study are outlined below.

2.1 EFFICACY OBJECTIVES

2.1.1 Primary Efficacy Objective

The primary efficacy objective for this study is to evaluate the efficacy of MSTT1041A compared with placebo on the basis of the following endpoint:

[figure not shown]
- Percent change from baseline to Week 16 of total Eczema Area and Severity Index (EASI) score

2.1.2 Secondary Efficacy Objective

The secondary efficacy objective for this study is to evaluate the efficacy of MSTT1041A compared with placebo on the basis of the following endpoints:

- Proportion of patients who achieve IGA response of 0 or 1 (clear or almost clear) at Week 16
- Proportion of patients who achieve EASI-75 ($\geq 75\%$ reduction from baseline in EASI score) at Week 16
- Percent change in pruritus from baseline to Week 16, as assessed by a Numeric Rating Scale (NRS)
- Percent change in body surface area (BSA) with AD involvement from baseline to Week 16
- Percent change in disease severity from baseline to Week 16, as assessed by SCORing Atopic Dermatitis (SCORAD)

2.2 SAFETY OBJECTIVE

The safety objective for this study is to evaluate the safety of MSTT1041A compared with placebo on the basis of the following endpoints:

- Incidence and severity of adverse events, with severity determined according to the WHO toxicity scale
- Change from randomization visit in vital signs, ECGs, and clinical laboratory results

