3. STUDY DESIGN

3.1 DESCRIPTION OF THE STUDY

This is a Phase II, randomized, double-blind, placebo-controlled multicenter study to assess the efficacy and safety of MSTT1041A in patients with moderate to severe AD. The study will consist of a screening period (Day -35 to -1), 16-week double-blind treatment period, and an 8-week follow-up period.

After providing informed consent, patients will be assessed for study eligibility during screening and at the randomization (Day 1) visit. Screening will be up to 35 days. During the screening period, patients must demonstrate EASI score ≥ 16 , IGA score ≥ 3 , pruritus NRS score for maximum itch intensity ≥ 3 , and have a history of inadequate response to treatment with topical medications. Furthermore, patients will be required to apply moisturizers (emollients) at least twice daily and to refrain from TCS or TCI use for at least the 7 consecutive days immediately before randomization and throughout the study. However, to allow adequate assessment of skin dryness, moisturizers should not be applied on the area(s) of non-lesional skin designated for such assessments for at least 8 hours before each office visit (see Sections 4.1.1 and 4.1.2 for details). Patients who fail to meet eligibility criteria during screening will be permitted to re-screen once, unless the reason for the screen failure is because of not meeting any of the following:

- EASI score ≥ 16 at screening and the randomization visit
- IGA score ≥ 3 (on the 0 to 4 IGA scale, in which 3 is moderate and 4 is severe) at screening and the randomization visit
- $\geq 10\%$ BSA of AD involvement at screening and the randomization visit
- Baseline pruritus NRS score for maximum itch intensity ≥ 3 at screening and the randomization visit

Patients who fail to meet eligibility requirements and are eligible to be re-screened are required to repeat assessments as follows:

- If ≤ 35 days after Informed Consent Form completion, repeat only the assessments that triggered screen failure.
- If > 35 days after Informed Consent Form completion, repeat the consent process and all screening assessments except tuberculosis (TB) screening and hepatitis serologies. TB screening and hepatitis serologies should be repeated if re-screening occurs > 3 months after initial Informed Consent Form completion.

[figure not shown]
At Day 1, patients will undergo further assessments to determine eligibility for randomization to the double-blind treatment period.

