4.1.1 Inclusion Criteria

Patients must meet the following criteria for study entry:

- Signed Informed Consent Form
- Age 18–75 years at time of signing Informed Consent Form
- Body mass index of 18–40 kg/m² and weight \geq 40 kg at screening
- Ability to comply with the study protocol, in the investigator's judgment

- Ability to understand and complete study-related questionnaires
- Chronic AD, (according to American Academy of Dermatology Consensus Criteria [Eichenfield et al. 2014]), that has been present for at least 3 years before the screening visit
- EASI score ≥ 16 at screening and the randomization (Day 1) visit
- IGA score ≥ 3 (on the 0 to 4 IGA scale, in which 3 is moderate and 4 is severe) at screening and the randomization (Day 1) visit
- $\geq 10\%$ BSA of AD involvement at screening and the randomization (Day 1) visit
- Pruritus NRS score for maximum itch intensity ≥ 3 at screening and the randomization (Day 1) visit
- Documented recent history (within 6 months before the screening visit) of inadequate response to treatment with topical medications or for whom topical treatments are otherwise medically inadvisable (e.g., because of important side effects or safety risks)

Inadequate response is defined as failure to achieve and maintain remission or a low disease activity state (comparable to IGA 0=clear to 2=mild) despite treatment with a daily regimen of TCS of medium to higher potency (\pm TCI as appropriate), applied for at least 4 weeks or for the maximum duration recommended by the product prescribing information (e.g., 2 weeks for ultra-high potent TCS; see [Appendix 2](#)), whichever is shorter.

Patients with documented systemic treatment (e.g., oral, IV) for AD at any point during the past 6 months are also considered as inadequate responders to topical treatments and are potentially eligible for the study after appropriate washout.

Important side effects or safety risks are those that outweigh the potential treatment benefits and include intolerance to treatment, hypersensitivity reactions, significant skin atrophy, and systemic effects, as assessed by the investigator or by the patient's treating physician.

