4.1.2 Exclusion Criteria

Patients who meet any of the following criteria will be excluded from study entry:

- Pregnant or breastfeeding, or intending to become pregnant during the study or within 12 weeks after the final dose of study drug

Women of childbearing potential must have a negative serum pregnancy test result during the screening period and a negative urine pregnancy test at the randomization visit

- Prior treatment with MSTT1041A

- Use of any of the following:

Treatment with any investigational therapy (with the exception of biologics) within 8 weeks or within 5 half-lives (if known), whichever is longer, before screening

Treatment with immunomodulatory, immunosuppressive (e.g., systemic corticosteroids, methotrexate, mycophenolate-mofetil, IFN- γ , Janus kinase inhibitors, cyclosporine, azathioprine, etc.) within 4 weeks before screening or any condition (e.g., severe asthma) that, in the opinion of the investigator, is likely to require such treatment during the course of the study

Treatment with investigational or licensed biologics as follows:

- Any cell-depleting agents including but not limited to rituximab: within 6 months before screening, or until lymphocyte count returns to normal, whichever is longer
- Other biologics: within 3 months or 5 half-lives (if known) before screening, whichever is longer

- Use of any of the following treatments within 2 weeks before screening, or any condition that, in the opinion of the investigator, is likely to require such treatment during the course of the study:

Regular use (more than 2 visits per week) of a tanning booth/parlor

Phototherapy

- Treatment with TCS or TCIs within 1 week before the randomization (Day 1) visit
- Initiation of treatment for AD with prescription moisturizers or moisturizers containing additives such as ceramide, hyaluronic acid, urea, or filaggrin degradation products within 1 week before the randomization (Day 1) visit
- Initiation of or change in allergen immunotherapy within 12 weeks before screening
- Use of any of the following treatments within 4 weeks before screening, or any condition that, in the opinion of the investigator, is likely to require such treatment during the course of the study:

Treatment with immunoglobulin or blood products

Treatment with any live, attenuated vaccine

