4.5.6 Laboratory, Biomarker, and Other Biological Samples

Samples for the following laboratory tests will be sent to the study site's local laboratory for analysis or analyzed at point of care:

- Urine pregnancy test for all women of childbearing potential

Urine pregnancy tests will be performed at the site prior to each administration of study drug and at other specified visits after treatment discontinuation. If a local urine pregnancy test result is positive, it must be reported immediately, and study drug will not be administered that day. The positive urine pregnancy result must be confirmed by a serum pregnancy test (conducted by the central laboratory). Refer to Section 5.4.3.1 for management of a patient with a positive pregnancy test.
- TB tests: PPD or QFT (QFT may be conducted by the central laboratory, per Sponsor agreement with site)

Samples for the following laboratory tests will be sent to one or several central laboratories for analysis:

- Hematology: WBC count, RBC count, hemoglobin, hematocrit, platelet count, and differential count (neutrophils, eosinophils, basophils, monocytes, lymphocytes, other cells)
- Chemistry panel (serum or plasma): bicarbonate or total carbon dioxide (if considered standard of care for the region), sodium, potassium, chloride, glucose, BUN or urea, creatinine, total protein, albumin, phosphorus, calcium, total and direct bilirubin, ALP, ALT, AST
- Fasting lipids: total cholesterol, LDL cholesterol, HDL cholesterol, triglycerides
- Fasting glucose
- HbA_{1c}
- N-terminal pro B-type natriuretic peptide
- Serum pregnancy test
- Urinalysis, including dipstick (pH, specific gravity, glucose, protein, ketones, blood) and microscopic examination (sediment, RBCs, WBCs, casts, crystals, epithelial cells, bacteria)

- Viral serology: HBsAb, HBsAg, HBCAb, HCV antibody
 - If HBsAb testing is positive and HBCAb is positive, patient must undergo further testing for HBV DNA.

Blood samples will be collected to evaluate the pharmacokinetics of MSTT1041A in serum as noted in the schedule of activities (see [Appendix 1](#)). Serum concentrations of MSTT1041A will be determined using validated analytical procedures.

The following samples will be sent to the Sponsor or a designee for analysis:

- Serum samples for MSTT1041A PK analysis
- Serum samples for immunogenicity analysis
- Serum samples for specific IgE, and total IgE, and other biomarkers; mandatory blood

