4.5.7 Electrocardiograms

Single ECG recordings will be obtained at specified timepoints, as outlined in the schedule of activities (see [Appendix 1](#)), and may be obtained at unscheduled timepoints as indicated.

All ECG recordings must be performed using a standard high-quality, high-fidelity digital electrocardiograph machine equipped with computer-based interval measurements. Lead placement should be as consistent as possible. ECG recordings must be performed after the patient has been resting in a supine position for at least 10 minutes. All ECGs are to be obtained prior to other procedures scheduled at that same time (e.g., blood draws). Circumstances that may induce changes in heart rate, including environmental distractions (e.g., television, radio, conversation) should be avoided during the pre-ECG resting period and during ECG recording.

For safety monitoring purposes, the investigator must review, sign, and date all ECG tracings. Paper copies of ECG tracings will be kept as part of the patient's permanent study file at the site. Digital recordings will be stored at central ECG laboratory, and the data will be sent to the Sponsor, using the Sponsor's standard procedures to handle and process the electronic transfer of these data. Any clinically significant morphologic waveform changes or other ECG abnormalities must be documented on the appropriate eCRF. If considered appropriate by the Sponsor, ECGs may be analyzed retrospectively at a central laboratory.

If at a particular postdose timepoint the mean QTcF is > 500 ms and/or > 60 ms longer than the baseline value, another ECG must be recorded, ideally within the next 5 minutes, and ECG monitoring should continue until QTcF has stabilized on two successive ECGs. The same procedure should be repeated approximately 30 minutes after QTcF has stabilized on two successive ECGs of the first measurement. The Medical Monitor should be notified. Standard-of-care treatment may be instituted per the discretion of the investigator. If a PK sample is not scheduled for that timepoint, an unscheduled PK sample should be obtained. A decision on study drug discontinuation should be made, as described in Section [5.1.2.3](#). The investigator should also evaluate the patient for potential concurrent risk factors (e.g., electrolyte abnormalities, co-medications known to prolong the QT interval, severe bradycardia).

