
Appendix 1: Schedule of Activities

	SCR	Treatment Period												FU	EOS	
		V1	V2	V3	V4	V5	V6	V7	V8	V9	V10	V11	V12			
Visit																
Week	D –35 to –1	D1	W1	W2	W4	W6	W8	W10	W12	W14	W16	W20	W24			
			D8	D15	D29	D43	D57	D71	D85	D99	D113	D141	D169			
(Visit window in days)			(± 2)	(± 3)	(± 4)	(± 4)	(± 4)	(± 4)	(± 4)	(± 4)	(± 4)	(± 4)	(± 5)	(± 5)	ET ^a	UV ^b
Office/Phone visit	O	O	O	O or P	O	P	O	P	O	P	O	P	O	O	O	O
Vital signs ⁱ	x	x	x		x		x		x		x		x	x	x	
ECG (12-lead, single)	x						x				x		x	x	x	
Serum pregnancy test ^j	x															x
Urine pregnancy test ^j		x	x		x		x		x		x		x	x	x	
Hepatitis B/C serology	x															
Hepatitis B DNA	x										x			x		
TB test	x															
Chest X-ray, TB worksheet ^k	x															
Hematology ^l	x	x	x		x		x		x		x		x	x	x	
Chemistry ^m	x	x			x		x		x		x		x	x	x	
NT-proBNP		x													x ⁿ	
Urinalysis ^o	x	x									x			x		
HbA ₁ C	x										x		x	x	x	
Fasted glucose and lipids ^p		x									x		x	x	x	
Serum PK ^q		x	x		x		x		x		x		x	x	x	
Serum specific IgE		x														

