Appendix 1: Schedule of Activities

- As clinically indicated.
- Urinalysis includes dipstick (pH, specific gravity, glucose, protein, ketones, blood) and microscopic examination (sediment, RBCs, WBCs, casts, crystals, epithelial cells, bacteria).
- If patient has not fasted for 8 hours, the patient must return to the site for fasting blood draw only. All other visit assessments should be completed within the regular visit.
- PK and ADA samples to be collected prior to study drug administration.
[REDACTED]
- Patients will receive 490 mg MSTT1041A or placebo at Day 1, Week 4, 8, and 12 visits administered as four SC injections (one in each quadrant of the abdomen). The dose at the Week 1 visit will be 245 mg MSTT1041A or placebo (loading dose) administered as two SC injections (see Section 4.3.2.1 for details).
- Medication (e.g., prescription drugs, over-the-counter drugs, vaccines, herbal or homeopathic remedies, nutritional supplements, emollients) used by a patient in addition to protocol-mandated treatment from 6 months before screening until 12 weeks after the final dose of study drug.
- After informed consent has been obtained but prior to initiation of study drug, only serious adverse events caused by a protocol-mandated intervention should be reported. After initiation of study drug, all adverse events will be reported until 12 weeks after the after the final dose of study drug. After this period, the Sponsor should be notified if the investigator becomes aware of any serious adverse event that is believed to be related to prior study drug treatment (see Section 5.6).

[figure not shown]
Appendix 2

WHO Classification of Topical Corticosteroids

The following table provides a non-exhaustive list of examples of topical corticosteroids classified by potency (Source: <http://apps.who.int/medicinedocs/en/d/Jh2918e/32.html>).

Potency	Class	Topical Corticosteroid	Formulation
Ultra High	I	Clobetasol propionate	Cream, 0.05%
		Diflorasone diacetate	Ointment, 0.05%
High	II	Amcinonide	Ointment, 0.1%
		Betamethasone dipropionate	Ointment, 0.05%
		Desoximetasone	Cream or ointment, 0.025%
		Fluocinonide	Cream, ointment or gel, 0.05%
		Halcinonide	Cream, 0.1%
		Betamethasone dipropionate	Cream, 0.05%
		Betamethasone valerate	Ointment, 0.1%
		Diflorasone diacetate	Cream, 0.05%
		Triamcinolone acetonide	Ointment, 0.1%
		Desoximetasone	Cream, 0.05%
		Fluocinolone acetonide	Ointment, 0.025%
		Fludroxcortide	Ointment, 0.05%
		Hydrocortisone valerate	Ointment, 0.2%

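### Is the ECG change endpoint left without a reference value because Appendix 1 shows no Day 1 ECG?

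*Combined protocol and SAP*

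**What the plan says.** Section 2.2 and the safety objective in the synopsis list, as one safety endpoint, "Change from randomization visit in vital signs, ECGs, and clinical laboratory results". The inclusion criteria in Section 4.1.1 show that randomization is a separate visit from screening: several disease criteria must be met "at screening and the randomization (Day 1) visit". Section 3.1 places screening between Day -35 and Day -1.

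ECG timing is delegated to Appendix 1. Section 4.5.7 says: "Single ECG recordings will be obtained at specified timepoints, as outlined in the schedule of activities". Unscheduled recordings are allowed where indicated.

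Section 6.5 plans descriptive statistics for ECGs by treatment group at each visit. It plans no ECG hypothesis test and gives no rule for which ECG serves as reference. Sections 4.5.7 and 5.1.2.3 compare QTcF with a baseline value and do not name the visit it comes from.

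**The concern.** If the reference for ECG change is the Day 1 visit and no ECG is scheduled then, the endpoint as worded cannot be computed from scheduled data. ECG assessment is among the tools that Section 5.1.1.5 names for evaluating cardiac safety, so a missing reference would matter more here than for a routine laboratory value. Nothing in the protocol says that the screening ECG may stand in. The study report would have to depart from its own endpoint definition, and an unstated reference can in principle leave room for choice after the data are seen.

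**Working it through.** No sample size or power figure is involved. The check sets the endpoint beside the schedule and asks what an analyst could compute.

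**1. Reading the ECG row.** The week line of that page of Appendix 1 gives the column order: screening, Day 1, Weeks 1, 2, 4, 6, 8, 10, 12, 14, 16, 20, 24, then early termination and unscheduled visits.

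| Row (same page) | Marks |
|---|---|
| ECG | screening, W8, W16, W24, and two right-edge columns |
| Vital signs | screening, D1, W1, W4, W8, W12, W16, W24, and two right-edge columns |
| Hematology | as vital signs |
| Chemistry | as vital signs, without W1 |

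The Day 1 gap is therefore in the ECG row and not in the main companion measures of the endpoint. HbA1c shows the same gap, but the laboratory summaries in Section 6.5 name only hematology and serum chemistry.

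**2. Can the blank cell be trusted?**

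- In favour: 9 of the 16 rows on the page carry a Day 1 mark in the right column. Section 4.5.6 says "Urine pregnancy tests will be performed at the site prior to each administration of study drug", and the Appendix 1 footnote says "Patients will receive 490 mg MSTT1041A or placebo at Day 1, Week 4, 8, and 12 visits", with the loading dose at Week 1. The urine pregnancy row is marked at all 5 of those visits. The 8 screening or Day 1 cells on the page that Sections 4.1.2 and 5.1.2.2 fix also match.
- Against: on the next page, Randomization and the first ADA sample fall under Week 1 with Day 1 blank, although Section 4.2 puts randomization on the first dosing day and calls for baseline ADA samples. On the previous page, limited physical examination falls under Week 20, a telephone visit. The ECG page itself has 16 office/phone entries against 15 on the previous page, and eight (± 4) windows where Weeks 4 to 16 need seven. No text outside the table fixes any ECG cell.

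A displaced mark would not supply both a screening and a Day 1 ECG, because the row has only one mark before Week 8. A lost mark would, and the text cannot rule that out.

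**3. If the cell is truly blank, what can be computed?**

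- Scheduled ECGs before the first dose: 1 (screening).
- Change values as literally worded: 0.
- Change values against screening for a patient who completes the study: 3 (Weeks 8, 16 and 24).
- Age of the reference: with no Day 0, Day -k lies k days before Day 1, so 1 to 35 days. It could be older after re-screening, because within 35 days of consent Section 3.1 repeats only the failed assessments.

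**4. Does the older reference distort the comparison?** Write the change as

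Y(post) − Y(screening) = [Y(post) − Y(Day 1, pre-dose)] + [Y(Day 1, pre-dose) − Y(screening)].

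The second bracket is settled before any study drug is given. Under randomization its expected value is the same in both arms, so it cancels from the difference between arms. It can add noise to individual changes and shift both arms alike, but it creates no bias between them.

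**The case for a change.** The case for acting is fair. The endpoint names a visit, the schedule shows no ECG there, and no sentence connects the two. The faults on the next page look like marks that moved rather than vanished, and the ECG row has no stray Week 1 mark, so a true blank is the likelier reading. The repair would be a few words and no new procedure. That much stands: if the original page confirms the blank, endpoint and schedule do not match.

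What does not stand is that anything turns on it. With one scheduled pre-dose ECG there is little to choose among. The screening value is the only candidate unless a patient happens to have an unscheduled pre-dose recording, in which case the last value before first dose is the ordinary convention. The planned summaries are descriptive and by visit.

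The QTcF rules are a separate matter. Sections 4.5.7 and 5.1.2.3 rely on a baseline value tied to no visit, and Section 4.5.7 refers to a mean QTcF although single recordings are scheduled. Those passages must be reconciled with each other and with Appendix 1 by the sponsor. They govern clinical management, so nothing is said here about which baseline should apply, and they do not bear on the statistical endpoint.

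**Conclusion.** No change to the analysis plan follows. At most, the words randomization visit were applied to a group of safety measures of which one, the ECG, has its only scheduled pre-dose value at screening. Analysts would fill that gap in the one available way, at a cost of a reference normally 1 to 35 days old. Both arms are affected alike, ECG results are only described, and efficacy and power are unaffected. Rewording the endpoint would alter neither the data collected nor any result.

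This rests on three assumptions: that the Day 1 ECG cell is blank on the original page (if it is marked, there is no mismatch at all); that the screening ECG is taken for essentially every randomized patient, as scheduled; and that the ECG analysis stays descriptive as in Section 6.5. A formal ECG comparison would call for a stated reference, but none is planned.
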